2.4.2 Prior, concomitant and post therapies

Prior and Concomitant medications will be coded using the World Health Organization (WHO) Drug Reference List (DRL) dictionary that employs the WHO Anatomical Therapeutic Chemical (ATC) classification system using the latest version available prior to clinical database lock and summarized by lowest ATC class and preferred term.

The ATC class will be presented in alphabetical order. Preferred terms will be sorted by decreasing proportion and alphabetical order.

Prior medications are defined as treatments taken and stopped prior to first dose of study treatment.

Concomitant therapy is defined as all interventions (therapeutic treatments and procedures) other than the study treatment administered to a subject coinciding with the study treatment period. Concomitant therapy includes medications (other than study treatments) starting on or after the start date of study treatment or medications starting prior to the start date of study treatment and continuing after the start date of study treatment.

Summaries for concomitant medications will include:

1. Medications starting on or after the start of study treatment but no later than 105 days after start of last dose of study treatment and
2. Medications starting prior to start of study treatment and continuing after the start of study treatment.

Medications will be presented in alphabetical order, by Anatomical Therapeutic Classification (ATC) codes and grouped by anatomical main group. Tables will show the overall number and percentage of subjects receiving at least one treatment of a particular ATC code and at least one treatment in a particular anatomical main group.

Prior and concomitant medications for analgesics and hydroxyurea will be summarized separately.

Prior and concomitant non-drug therapies/procedures will be summarized according to the Anatomical Therapeutic Chemical (ATC) classification system for all subjects.

All prior and concomitant therapies will be listed. Any concomitant therapies starting and ending prior to the start of study treatment or starting more than 105 days after the last date of study treatment will be flagged in the listing. The safety set will be used for all concomitant medication tables and listings.

Rescue medications

Rescue medication is defined as medication used to control symptoms that are not adequately controlled on study treatment.

As per protocol, any standard medications that are used for management of VOC [REDACTED] [REDACTED] should follow the recommendation from [name] publication (Minniti et al 2010). Thus, these medications will be identified by the medical team and provided for analysis.

Rescue medication will be summarized similarly to concomitant medication.

2.5 Analysis supporting primary objective(s)

The primary objective of this study is to evaluate clinical efficacy of crizanlizumab 5 mg/kg, over 26 weeks compared to baseline in sickle cell subjects with a history of priapism.

2.5.1 Primary endpoint(s)

The primary endpoint of the study is percent reduction from baseline in priapism events by 26 weeks (i.e., up to pre-infusion Week 27 Day 1). Priapism event is defined as unwanted, or painful erection lasting at least 60 minutes, self-reported.

Percentage change from baseline = (Post baseline value –Baseline value) * 100 / Baseline value; (relative change from baseline).

Percentage reduction from baseline is the negative percentage change from baseline.

2.5.2 Statistical hypothesis, model, and method of analysis

It is expected that crizanlizumab treatment reduces priapic events by at least 25% in SCD subjects with priapism.

Demonstration of significant percent reduction from baseline in priapic events will be evaluated using following hypothesis:

$H_0: p < 0.25$, where p is the percent reduction in priapic events by 26 weeks.

$H_1: p \geq 0.25$, where p is the percent reduction in priapic events by 26 weeks.

If the above null hypothesis is rejected, significant reduction in priapic events will be demonstrated statistically.

Assuming uniformity in the occurrence of priapic events before exposure to crizanlizumab treatment, baseline will be adjusted for 26 weeks for analysis purpose.

Baseline (adjusted for 26 weeks): Number of priapic events in 12 weeks screening period * (26/12) and percentage change from baseline = (Post baseline value –Baseline (adjusted to 26 weeks) value) * 100 / Baseline (adjusted to 26 weeks) value.

Percentage reduction from baseline is the negative percentage change from baseline.

Percent reduction from baseline in priapic events will be tested using a non-parametric test (i.e., Wilcoxon's Sign Rank test) and p-value will be reported. The study would be declared a success, if percentage reduction in events is $\geq 25\%$ and $p < 0.05$ is obtained from Wilcoxon's Sign Rank test.

Hodges-Lehmann estimate of median percent reduction in priapic events will also be reported, along with corresponding 95% confidence intervals.

Number of priapic events will be summarized at baseline (adjusted for 26 weeks) and by Week 26, and percent reduction from adjusted baseline by Week 26 will be summarized by n, mean, standard deviation (SD), lower quartile (Q1), median, upper quartile (Q3), minimum and maximum.

Graphical representation of percentage reduction, through box plot or bar graph or waterfall plot, will be performed as appropriate by 26 weeks.

In addition, subgroup analysis of the primary endpoint will be performed based on the number of priapic events categories (i.e. <7, 7 - 13, 14 - 21, \geq 22) at baseline (12 weeks) and baseline (adjusted for 26 weeks). Additional analyses of the primary endpoint will also be performed for the subgroups of subjects with stuttering and acute priapism. Summary statistics for percentage reduction by 26 weeks will be presented for each subgroup.

The priapic events categories may be re-grouped to ensure that there is adequate number of subjects in each category for analysis. Additional analyses will also be performed for the subgroups of subjects with acute priapism and subjects who have experienced priapic episodes lasting less than one hour.

The primary analysis will be performed only on all FAS subjects who have completed 26 weeks on treatment.

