### **12.4.2 Statistical model, hypothesis, and method of analysis**

It is expected that crizanlizumab treatment reduces priapic events by at least 25% in SCD subjects with priapism. Demonstration of significant percent reduction from baseline in priapic events will be evaluated using the following hypothesis:

$H_0: p < 0.25$ , where  $p$  is the percent reduction in priapic events by 26 weeks.

$H_1: p \geq 0.25$ , where  $p$  is the percent reduction in priapic events by 26 weeks.

If the above null hypothesis is rejected, significant reduction in priapic events will be demonstrated statistically.

Assuming uniformity in the occurrence of priapic events before exposure to crizanlizumab treatment, baseline will be adjusted for 26 weeks for analysis purpose.

Percent reduction from baseline in priapic events will be tested using a nonparametric test (i.e. Wilcoxon's Sign Rank test). Hodges-Lehmann estimate of median percent reduction in priapic events will also be reported, along with corresponding 95% confidence intervals. The significance of the efficacy endpoints will be assessed at  $\alpha = 0.05$  level.

The primary analysis will be performed on all FAS subjects who have completed 26 weeks on treatment.

Number of priapic events will be summarized at baseline (adjusted for 26 weeks) and by Week 26, and percent reduction from adjusted baseline by Week 26 will be summarized by mean, standard deviation (SD), lower quartile (Q1), median, upper quartile (Q3), minimum and maximum. In addition, subgroup analysis of the primary endpoint will also be performed based on the number of priapic events categories (i.e.  $<7$ ,  $7 - 13$ ,  $14 - 21$ ,  $\geq 22$ ) at baseline. The priapic events categories may be re-grouped to ensure that there is adequate number of subjects in each

category for analysis. Additional analyses will also be performed for the subgroups of subjects with acute priapism and subjects who have experienced priapic episodes lasting less than one hour.

Further details will be provided in the SAP.

The imputation of missing data caused by intercurrent events will be handled by defining the estimand framework. The primary estimand is described by the following four attributes:

1. The target population comprises Sickle Cell Disease Patients with Priapism
2. The primary variable is percent reduction from baseline period in priapic events (priapism defined as unwanted, or painful erection lasting at least 60 min self-reported) by 26 weeks.

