## **12.9 Sample size calculation**

A total of 34 evaluable subjects is required for the study to have approximately 80% power to detect at least 25% reduction in rates of priapic events (defined as an unwanted erection lasting at least 60 min reported via daily diary tool) with a mean baseline priapism event rate of 10.0 and standard deviation of the difference of 5.0, by 26 weeks.

The calculations were based on simulation with 5,000 repetitions (from Poisson distribution) using one-sample Wilcoxon's Signed-Rank Test and 2-sided  $\alpha=0.05$ .

Retaining the same above assumptions, robustness of the estimated sample size was also validated using a one-sample t test.

Assuming a 5% dropout rate, approximately 36 subjects will be enrolled in the study.

Recruitment of the required number of subjects with priapism will be challenging as the incidence of priapic events are sporadic and varies over time intervals. Also, in the absence of relevant clinical data on priapism, the expected reduction and higher variability in events rates have been conservatively assumed. The above expected 25% reduction in rates of priapic events from baseline is based on medical expert opinion and feedback. L-glutamine (EndariTM) was approved by the US FDA in July 2017 for the reduction of vaso-occlusive crises (VOCs), based on a 25% reduction. Since priapism is also considered to be a complicated VOC, the assumption was that the relative risk reduction of 25% (approved for VOC events), would be similar for priapism.

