2.5.3 Handling of intercurrent events

The imputation of missing data caused by intercurrent events will be handled by defining the estimand framework.

The primary estimand is described by the following four attributes:

1. The target population comprises Sickle Cell Disease Patients with Priapism.
2. The primary variable is percent reduction from baseline period in priapic events (priapism defined as unwanted, or painful erection lasting at least 60 min self-reported) by 26 weeks.
3. Treatment of interest: investigational drug will be a crizanlizumab solution provided every 4 weeks with an additional loading dose 2 weeks after the first dosing.
4. The intercurrent events are the events occurring after enrollment that may impact the treatment effect. The intercurrent events of interest are listed below:
 - a. Treatment discontinuation
 - b. Initiation or discontinuation of HU/HC or l-Glutamine (or other therapies to treat SCD and or to prevent/reduce VOCs such as voxelotor and erythropoietin) or of prophylactic treatment for priapism
 - c. Intake of analgesic (including opioids) or ad hoc transfusions administered temporarily
5. The summary measure is the median percentage change from baseline period in priapic events (priapism defined as unwanted, or painful erection lasting at least 60 min self-reported) by 26 weeks.

Handling of the intercurrent events:

The approach of accounting for intercurrent events is as follows:

- **For the intercurrent events 4a:** Only data before study treatment discontinuation will be included. The data between treatment discontinuation and week 26 will be imputed using Poisson distribution (primary method to handle missing data as described in [Section 2.5.4](#)).
- **For the intercurrent events 4b:** Only data before initiation or discontinuation of HU/HC or L-Glutamine (or other therapies to treat SCD and or to prevent/reduce VOCs such as Voxelotor and erythropoietin) or of prophylactic treatment for priapism will be included. The data between initiation or discontinuation of therapies to treat SCD or of prophylactic treatment for priapism and week 26 will be imputed using Poisson distribution (primary method to handle missing data as described in [Section 2.5.4](#)).
- **For the intercurrent events 4c:** Data after intake of analgesic (including opioids) or ad hoc transfusions administered temporarily will be included (treatment policy strategy).

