5.4 Statistical models

5.4.1 Analysis supporting primary objective(s)

Primary analysis

Wilcoxon signed rank test

The SAS procedure PROC UNIVARIATE will be used to perform Wilcoxon signed-rank test.

Hodges-Lehmann Estimation

The SAS procedure PROC NPAR1WAY will be used to compute the Hodges-Lehmann estimate.

Handling of missing data

Generating the multiple imputation

The missing values will be imputed for the primary analysis.

- To fill in the missing values (i.e. number of priapic events by 26 weeks), generate Poisson distributed random variables with a rate parameter based on the same effect as observed data. Compute 1000 such complete datasets. Use seed 10105.
- Each datasets will be analyzed using the same method as described in primary analysis.

Analyzing the imputed data

- The resulting estimates and standard errors will be combined using Rubin's rule ([Barnard J and Rubin DB 1999](#)), by the SAS procedure MIANALYZE.

Tipping point analysis for priapic events by 26 weeks

As a sensitivity analysis to evaluate the impact of missing data, a tipping point analysis will be performed for the primary endpoint.

The primary endpoint will be re-analyzed on the delta-adjusted datasets to see if the conclusions change. If not, a larger delta is chosen and the process will be repeated until the conclusion is overturned. The tipping point is the delta value which will cause the primary endpoint to be no longer statistically significant. A series of analyses on a range of delta values (i.e., 1,2,3,.....) will be performed to find the tipping point.

For each delta value, the following steps will be performed.

1. Impute the missing values (i.e. number of priapic events by 26 weeks) by generating Poisson distributed random variables with a rate parameter based on the same effect as observed data. Use seed 10105.
2. After the imputation obtained in above step, make the imputed value worse by a value of delta (i.e., add delta to the imputed value). Note: delta = 0 represents the standard missing at random (MAR).
3. The final imputed delta-adjusted dataset where all missing values are filled, will be analyzed using method as described in the primary analysis.

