4. The results from the 1000 delta-adjusted datasets will then be combined using Rubin's rule. If the combined results does not change the conclusion (i.e., if percentage reduction in events is $\geq 25\%$ statistically significant), a larger delta will be chosen and Steps 1-4 will be repeated using the datasets from Step 1 until the tipping point is found (when $p > 0.05$).

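### The 25% null hypothesis, the 80% power (which reproduces only against zero) and the SAP's two-part success rule are three different tests, so 80% is not the chance of declaring success

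*SAP*

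**What the plan says.** - **Hypothesis.** Protocol 12.4.2 and SAP 2.5.2 write H0 as a reduction below 0.25 and H1 as 0.25 or more. Both add: "If the above null hypothesis is rejected, significant reduction in priapic events will be demonstrated statistically".
- **Sample size.** Protocol 12.9 and SAP 3 give 34 evaluable subjects for "approximately 80% power to detect at least 25% reduction in rates of priapic events". The baseline mean is 10.0, the SD of the difference is 5.0, and the signed-rank test is two-sided at 0.05. The expected true effect is also 25%.
- **Success rule (SAP 2.5.2 only).** "The study would be declared a success, if percentage reduction in events is" at least 25% and the signed-rank p-value is below 0.05.
- **Test.** SAP 5.4.1 gives the software and no null location: "The SAS procedure PROC UNIVARIATE will be used to perform Wilcoxon signed-rank test".
- **Estimate.** SAP 2.5.3 states: "The summary measure is the median percentage change from baseline period in priapic events". SAP 2.5.2 also reports a Hodges-Lehmann estimate, a mean and a median. The success sentence names none of them.
- **Tipping point (SAP 5.4.1).** One sentence defines it by significance alone: "The tipping point is the delta value which will cause the primary endpoint to be no longer statistically significant". Step 4 describes the unchanged conclusion as "If the combined results does not change the conclusion (i.e., if percentage reduction in events is" at least 25% and statistically significant, yet the search stops when p exceeds 0.05.

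**The concern.** The expected effect equals the boundary of the stated null. A valid test of that null has power equal to its size at the expected effect, whatever the N, so the 80% must belong to a different test. The success rule is a third decision, and its p-value has no stated reference value.

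Three things are at stake:
- A reader may take 80% as the chance that the primary analysis succeeds.
- A success under the rule could be reported as rejecting a reduction below 25%, which a test against zero does not do.
- With no estimate named, the success call stays open after the data are seen.

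**Working it through.** **Inputs** (Protocol 12.9, SAP 3): n = 34, baseline 10.0, SD of difference 5.0, two-sided alpha 0.05. A 25% reduction is 0.25 × 10.0 = 2.5 events, a standardised effect of 2.5/5.0 = 0.5.

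**1. Reproduce the 80%.** One-sample t test, null zero, noncentrality 0.5√n: power is 79.5% at n = 33 and 80.8% at n = 34. At n = 44 it is 90.0%, which matches the 44-subject, 90% design recorded in the summary of Amendment 2. The signed-rank test simulated at n = 34 (normal differences, 40,000 runs) gives 79.0%; count models with SD 5 give 79.1-80.8%. Independent Poisson counts of 10 and 7.5 have SD √17.5 = 4.2 and give 91.5%, so the SD of 5.0 drives the stated figure. Enrolment: 34/0.95 = 35.8, so 36. The plan's arithmetic is right for a null of zero.

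**2. Test the stated null instead.** At a true 25%, power against a 25% boundary is 2.5% (signed-rank simulation 2.6%). With n = 34 it reaches 80.8% only at a true 50%.

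**3. Two-part rule with a zero null.** The standard error of the percent reduction is 5/√34/10 = 8.57 points. The smallest observed mean reduction with p < 0.05 is 2.035 × 8.57 = 17.4%, so the 25% condition is the binding part. A symmetric estimate reaches its own true value half the time: P(estimate ≥ 25% | true 25%) = 0.50. For 80% the truth must be about 25 + 0.842 × 8.57 = 32.2%. Simulated success (normal differences, 40,000 runs per row):

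| True reduction | Mean | Hodges-Lehmann | Median |
|---|---|---|---|
| 0% | 0.2% | 0.2% | 0.5% |
| 15% | 12.2% | 12.7% | 15.4% |
| 20% | 27.9% | 28.5% | 30.4% |
| 24% | 45.6% | 45.5% | 45.0% |
| 25% | 50.0% | 49.8% | 48.8% |
| 32% | 79.4% | 78.9% | 74.6% |
| 34% | 85.1% | 84.5% | 79.9% |

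The 15%, 20% and 24% rows lie inside the stated H0.

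**4. Dependence on the model, at a true 25%.** Count models with SD 5 give 50-51% (mean), 52-53% (median) and 59% (Hodges-Lehmann). Independent Poisson counts give 50%, 55% and 62%. The SAP's actual endpoint is the per-subject percent reduction on baseline × 26/12, with entry requiring at least 4 events in 14 weeks, at least 3 in 12 weeks and at least 1 in the last 4 weeks. The documents do not fix its distribution, so the 26-week mean (10 or 20) and the spread (Poisson, or gamma with shape 2) are assumptions (4,000 runs each):

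| Scenario | Two-part, median, true 25% | Two-part, Hodges-Lehmann, true 25% | Test against zero alone, no effect | Two-part, median, no effect |
|---|---|---|---|---|
| Mean 10, Poisson | 88.9% | 82.7% | 16.1% | 3.8% |
| Mean 10, gamma | 79.7% | 68.5% | 7.9% | 0.8% |
| Mean 20, Poisson | 53.4% | 33.4% | 1.3% | 0.0% |
| Mean 20, gamma | 63.5% | 46.8% | 3.0% | 0.0% |

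The entry rule selects on high baselines, so apparent reductions arise without any drug effect. This is why the no-effect values here exceed those in step 3.

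**5. Tipping point.** In the design model an observed mean reduction between 17.4% and 25% is significant against zero but fails the success rule. A delta that moves the result into that band has overturned success, yet the search would continue because p is still below 0.05.

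**The case against.** The strongest reply is that the rule reads naturally as significance against zero plus a relevance threshold, and that quoting power for the test alone is ordinary practice. On this view the 2.5% branch is a strained reading, since a test centred at 25% would make the separate 25% condition largely redundant. That is fair, and the zero-null reading is the more plausible one. It still contradicts the written H0 and leaves the success probability unstated.

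Second, the 50% comes from a normal-difference model, not from the percent endpoint. With a mean of 10 and the median, success is 79.7-88.9%, close to or above 80%. The false-success rates inside H0 also move: a smaller run of the same four scenarios (1,500 repetitions each) gave 24-71% at a true 20% with the median and 10-59% with Hodges-Lehmann. This stands as a limit on the figures. It does not rescue the 80%, which was not calculated for this rule, and the 50% rests on the same baseline, SD and n as the 80%.

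Third, the median is the more lenient estimate at a true 25% in all four percent-endpoint scenarios. Restating H0 at zero also relaxes the written hypothesis after enrolment has closed in an open-label trial. Both should be disclosed. The median is the estimand's own summary measure, the 25% condition stays, and a claim of at least 25% would need the lower confidence limit.

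Fourth, SAP 2.5.2 describes Hodges-Lehmann as estimating the median percent reduction, so it does not contradict the estimand. Agreed: the gap is that the success sentence names no estimate.

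**Conclusion.** The concern holds. The mismatch between hypothesis, power basis and success rule is visible in the text and needs no simulation.

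Under the plan's own inputs with normal differences, the two-part rule succeeds about 50% of the time at a true 25%, against the quoted 80%. It reaches 80% at a true 32% (mean or Hodges-Lehmann) or 34% (median), and it succeeds 28-30% of the time at a true 20%. Centred at 25%, the test has about 2.5% power at the design effect.

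On the percent endpoint with the entry rule, success at a true 25% ranges from 53% to 89% (median) or 33% to 83% (Hodges-Lehmann) under the assumed rates. The exact probability is therefore uncertain, and agreement with 80% in some scenarios is coincidental. The rule decides the primary conclusion, so it must be corrected.

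**What to change.** - **Protocol 12.4.2, SAP 2.5.2 and 5.4.1:** state that the signed-rank null is zero reduction, and restate H0 as no reduction with 25% as the design alternative. Record when and why this was changed.
- **Success rule:** keep the observed reduction of at least 25% as a required second part. In the no-effect scenarios it lowers false success from 1-16% (test alone) to at most 4% (median). Tie it to the median percent reduction; if Hodges-Lehmann is preferred, align the estimand's summary measure.
- **Protocol 12.9 and SAP 3:** say that the 80% refers to the test against zero. Add the success probability of the two-part rule (about 50% at a true 25%, about 80% at 32-34%), labelled as conditional on the design model.
- **SAP 5.4.1, tipping point:** stop when either part of the success rule fails.
- **Reporting:** describe a reduction of at least 25% as statistically demonstrated only if the lower 95% confidence limit exceeds 25%.

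The cost is wording and a less favourable stated figure. There are no new patients or data, and N is unchanged. The protocol text needs a formal amendment with IRB approval (Protocol 14.1); until then SAP section 4 can record the change.

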### 2.1 Primary estimands

The estimand is the precise description of the treatment effect and reflects strategies to address events occurring during trial conduct which could impact the interpretation of the trial results (e.g. premature discontinuation of treatment).

The primary clinical question of interest is: What is the effect of crizanlizumab on reduction from baseline period in priapic events, by week 26?

The primary estimand is described by the following attributes:

1. Population: Sickle Cell Disease patients with priapism. Further details about the population are provided in [Section 5](#).
2. Endpoint: Percent reduction from baseline period in priapic events (priapism defined as unwanted, or painful erection lasting at least 60 min self-reported) by 26 weeks.
3. Treatment of interest: investigational drug will be a crizanlizumab solution provided every 4 weeks with an additional loading dose 2 weeks after the first dosing. Further details about the investigational treatment are provided in [Section 6](#).
4. List of intercurrent events:
  - a) Treatment discontinuation
  - b) Initiation or discontinuation of HU/HC or l-glutamine (or other therapies to treat SCD and or to prevent/reduce VOCs such as voxelotor and erythropoietin) or of prophylactic treatment for priapism as described in the [Sections 6.2.1, 6.2.2, 6.2.3](#)
  - c) Intake of analgesic (including opioids) or ad hoc transfusions administered temporarily as described in the [Section 6.5](#).
5. The summary measure: Median percentage change from baseline period in priapic events (priapism defined as unwanted, or painful erection lasting at least 60 min self-reported) by 26 weeks

Handling of intercurrent events is discussed in Section 12.4.2.

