### **3 Study design**

This is a multicenter, prospective, phase II, single-arm, open-label study to assess the efficacy and safety of crizanlizumab in SCD patients with priapism.

A total of approximately 36 male subjects aged  $\geq$  12 years, who meet all of the inclusion criteria and none of the exclusion criteria will be eligible for the study. Subjects with  $\geq$  4 priapic events during the 14 week pre-screening period and having at least 3 priapic events during the 12 week screening period with at least 1 event occurring within 4 weeks prior to the first treatment, will be included in the study.

The baseline period is defined as the 12 weeks screening period. Eligible subjects will be treated with crizanlizumab at a dose of 5.0 mg/kg. From the first screening visit until the end of follow-up, the total study duration will be up to 79 weeks (including 12 weeks of screening, 52 weeks of treatment and 15 weeks of follow-up as applicable). The primary analysis of the study will be conducted by 26 weeks to assess efficacy of crizanlizumab in those patient population, who have completed 26 weeks of treatment. The secondary [REDACTED] endpoints will be assessed by 26 weeks and/or 52 weeks. Subjects will be followed for safety for up to 105 days (15 weeks) after the last dosing if applicable. Subjects who will receive commercially approved

crizanlizumab approximately 4 weeks after their last dose of study treatment, do not need to complete the 105-day follow-up. The safety follow-up of these subjects will be at the End of Treatment (EOT) visit. All other subjects are required to complete the 105-day follow-up visit.

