1.1 Study design

[figure not shown]
This is a multicenter, prospective, phase II, single-arm, open-label study to assess the efficacy and safety of crizanlizumab in SCD (Sickle Cell Disease) subjects with priapism.

A total of approximately 36 male subjects aged ≥ 12 years, who meet all of the inclusion criteria and none of the exclusion criteria will be eligible for the study. Subjects with ≥ 4 priapic events during the 14 week pre-screening period and having at least 3 priapic events during the 12 week screening period with at least 1 event occurring within 4- weeks prior to the first treatment, will be included in the study.

The baseline period is defined as the 12 weeks screening period. Eligible subjects will be treated with crizanlizumab at a dose of 5.0 mg/kg. From the first screening visit until the end of follow-up, the total study duration will be 79-weeks (including 12 weeks of screening, 52 weeks of treatment and 15 weeks of follow-up period). The primary analysis of the study will be conducted by 26 weeks to assess efficacy of crizanlizumab in those subject population, who have completed 26 weeks of treatment. The secondary [REDACTED] endpoints will be assessed by 26 weeks and/or 52 weeks. Subjects will be followed for safety for up to 105 days (15 weeks) after the last dosing if applicable. Subjects who will receive commercially approved crizanlizumab approximately 4 weeks after their last dose of study treatment, do not need to

complete the 105-day follow-up. The safety follow-up of these subjects will be at the End of Treatment (EOT) visit. All other subjects are required to complete the 105-day follow-up visit.

Figure 1-1 Study design

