2.2 Analysis sets

The analysis sets to be used are defined as below.

All efficacy analyses will be performed on subjects in FAS who have completed treatment. The Safety Set will be used for all the safety analysis.

Full Analysis Set (FAS)

The FAS include all enrolled subjects to whom the study treatment has been assigned regardless of whether or not they have received at least 1 dose of study treatment or have at least 1 post-baseline assessment.

Safety Set (SAF)

The SAF will consist of all subjects who received at least 1 dose of study treatment.

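### The primary analysis set (26-week completers) contradicts the primary estimand, which keeps early stoppers and imputes their remaining time to Week 26

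*SAP*

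**What the plan says.** **Completer rule.** SAP 2.5.2: "The primary analysis will be performed only on all FAS subjects who have completed 26 weeks on treatment". Protocol 12.4.2 has the same restriction without the word only: "The primary analysis will be performed on all FAS subjects who have completed 26 weeks on treatment". Both study design sections agree, describing the aim as "to assess efficacy of crizanlizumab in those patient population, who have completed 26 weeks of treatment" (protocol Section 3) and "to assess efficacy of crizanlizumab in those subject population, who have completed 26 weeks of treatment" (SAP 1.1). SAP 2.2 and protocol 12.1 are wider in scope and give no time point: "All efficacy analyses will be performed on subjects in FAS who have completed treatment".

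**Estimand rule.** The population attribute in protocol 2.1 is "Population: Sickle Cell Disease patients with priapism", and SAP 1.2.1 and 2.5.3 match it. None of them mentions completion. Treatment discontinuation is intercurrent event 4a. For it, SAP 2.5.3 says "Only data before study treatment discontinuation will be included" and "The data between treatment discontinuation and week 26 will be imputed using Poisson distribution", labelled as the primary method for missing data. Protocol 12.4.2 has the same rule, and SAP 2.5.4 says that missing values are imputed for the primary analysis.

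**Elsewhere.** SAP Section 4, which lists departures from the protocol, does not mention the conflict. A repeat of the primary analysis on all FAS subjects appears only in the protocol summary.

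**The concern.** Two programmers, one following SAP 2.5.2 and the other SAP 2.5.3, would build different primary data sets. The first would drop every early stopper. The second would keep the stopper's observed events and impute the remainder.

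This is a single-arm, open-label trial. The success rule in SAP 2.5.2 (a reduction of at least 25% with p<0.05) would be applied to a set defined by something that happens after the first dose. Protocol 9.1.1 allows stopping for toxicity or by the subject's decision, so stopping may be related to outcome.

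The tipping-point analysis is a weak safeguard. SAP 2.5.5 runs it only if the amount of missing data is significant, and stoppers who are excluded beforehand may never count towards that condition.

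**Working it through.** **1. The plan's own numbers.** Inputs (protocol 12.9, SAP Section 3): mean baseline rate 10.0, reduction 25% (difference 2.5), SD of the difference 5.0, two-sided alpha 0.05, dropout 5%.
- Against a null difference of zero, one-sample t-test power at n = 34 is 80.8%. Wilcoxon signed-rank power by simulation on normal differences is 78.6%. Both agree with about 80%.
- Enrolment: 34 / 0.95 = 35.8, so 36.
- Expected dropouts: 36 × 0.05 = 1.8, about 2. Protocol 9.1.1 separates stopping treatment from leaving the study, so the number who stop treatment could differ.

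**2. The two rules applied to the same subject.** Take a subject whose last infusion is at Week 11 and who then stops treatment.
- Under SAP 2.5.2 he has not completed 26 weeks on treatment and contributes nothing.
- Under SAP 2.5.3 his events before stopping count, and the time from stopping to Week 26 is imputed.

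A subject who did complete 26 weeks has no discontinuation before Week 26, so rule 4a does not reach him. One edge case remains because completion is not defined. By the exposure formula in SAP 2.4.1 (last dose plus 27 days), a last infusion on Day 155 gives (155 + 27)/7 = 26.0 weeks, while SAP 2.1.1 ends study drug on Day 155. Rule 4a is therefore almost, but not strictly, empty.

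**3. Size at the planned dropout.** The documents give no outcome data for stoppers, so this is an illustration. Assumptions:
- 36 subjects, 2 stoppers; 2,000 simulated trials per scenario with 10 imputations each.
- 26-week rates gamma distributed (shape 4) with mean 10, or 10 × 26/12 = 21.7 if the planned rate is read as per 12 weeks.
- Poisson screening counts of at least 3, scaled by 26/12.
- Completers at 70% of their own rate; stoppers at 100% of theirs (no effect), leaving after 6 or 12 weeks.

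Gap = Hodges-Lehmann estimate in the 34 completers minus that in all 36, in percentage points:

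| Mean rate | Stop after | Rest imputed at completers' ratio | Rest imputed at own rate |
|---|---|---|---|
| 10 | 6 weeks | 0.29 | 0.78 |
| 10 | 12 weeks | 0.71 | 1.10 |
| 21.7 | 6 weeks | 0.33 | 1.06 |
| 21.7 | 12 weeks | 0.76 | 1.29 |

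If stoppers respond like completers, the gap is −0.21 to −0.09. The two imputation columns are both shown because SAP 2.5.4 and 5.4.1 tie the Poisson rate to the effect in the observed data without saying whose data.

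**4. Size with more stoppers.** With no-effect stoppers leaving at 12 weeks and own-rate imputation, the gap is about 2 points with 4 stoppers (4/36 = 11%), about 4 with 7 (19%) and 7 to 8 with 11 (31%). It is smaller if the remainder is imputed at the completers' ratio.

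**The case against.** **Completers may be what was meant.** The restriction stands in the same Amendment 3 protocol text as the estimand, the SAP sharpens it with the word only, and 34 evaluable subjects out of 36 fits a completer count. This stands as far as it goes: the contradiction runs both ways and the sponsor may choose. But the estimand population and rule 4a then cannot stay as written. Sensitivity analysis 2, which offers treatment policy for event 4a as an alternative to the primary handling, also makes little sense if no stopper is in the primary set.

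**Other text may resolve it.** SAP 2.1 and protocol Section 12 speak of all subjects' data at or up to Week 26. These are general statements and do not override the specific sentence in SAP 2.5.2. SAP 2.13 allows for separate SAP documentation for the primary analysis; if it exists, it cannot be seen here.

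**There is partial cover.** Sensitivity analysis 4 is run on the FAS, less subjects with COVID-related missing data, and the protocol summary has the all-FAS repeat. Neither is the primary analysis, and the repeat was not carried into the SAP.

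**Stronger readings that the documents do not support.**
- A reader might infer that the completer result is inflated, or cannot estimate the estimand at all. Rule 4a imputes on the assumption of the same effect as in the observed data, so if stoppers resemble completers the two analyses target nearly the same value. The documents do not say how many stop or why, so direction and size are unknown.
- A reader might infer that imputation is void altogether. It is not: event 4b and ordinary missing counts can occur in completers, and event 4c keeps its own rule.
- A reader might want a probability that the choice of set changes the trial's conclusion. Any such figure depends on how close the true reduction is to 25%, and one based on the estimate alone ignores the p<0.05 condition.

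**Conclusion.** The contradiction is real, appears in both documents, and is not reconciled in SAP Section 4. It should be fixed before the primary analysis is relied on. The primary result may be biased for the stated estimand if stoppers differ from completers.

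At the planned dropout the numerical effect is small: about 0.3 to 1.3 points if two stoppers had no benefit, and close to zero if they responded like the others. The range rests on the assumed rates, the 70% completer response and the imputation rate, none of which the documents supply. The main unknown is the number of stoppers. At around 20% to 30% discontinuation the gap could reach several points under the same unfavourable assumption.

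**What to change.** **Preferred.**
- Make the FAS the primary analysis set. If undosed subjects are to be left out, state that as a departure from the FAS definition.
- Use observed events up to discontinuation and impute only the remaining time to Week 26, as SAP 2.5.3 says. Align SAP 5.4.1, which describes the missing value as the whole 26-week count.
- State the imputation rate in SAP 2.5.4 and 5.4.1, for example the subject's adjusted baseline times the ratio observed in the analysis set. Show the subject's own on-treatment rate as a sensitivity analysis.
- Define completion of 26 weeks on treatment and keep the completer analysis as a sensitivity analysis. Say that sensitivity analyses 1 and 2 use the full set.
- Change SAP 1.1, 2.2 and 2.5.2 for the primary endpoint. State which set applies to the supportive analyses (SAP 2.5.6, protocol 12.4.4) and the secondary endpoints (SAP 2.6.1, protocol 12.5.1), which are also limited to completers.
- Record the change in SAP Section 4, or in a protocol amendment if protocol 14.1 requires one, as resolving a contradiction within Amendment 3. Give its date relative to any primary and final database lock.

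**If the sponsor wants completers.** Restate the estimand population, remove rule 4a, define completion, and bring the all-FAS repeat from the protocol summary into the SAP.

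Report both results in either case.

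**Cost.** Wording, modest reprogramming and no new data. The estimate may be slightly less favourable and will rest partly on imputed time. The change also comes late in an open-label trial. Enrolment was complete by 16-Dec-2022, and 12 + 26 = 38 weeks later is 8-Sep-2023, before the SAP of 20-Feb-2024. The dating therefore matters.
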